## 2. Secondary outcomes derivations and definitions

- a. EHR-based indication for increased cancer risk, defined separate for the time periods

- i. EHR-based variables
  - 1. Variable 1: Personal history code in EHR [Yes/No]
  - 2. Variable 2: Family history code in EHR [Yes/No]
  - 3. Variable 3: Other code in EHR [Yes/No]
- ii. Derived outcomes from the EHR-based variables
  - 1. Variable 4: number of Variables 1-3 with value = Yes
  - 2. Variable 5: at least 1 of Variables 1-3 is Yes
  - 3. Variable 6: number of Variables 1 and 2 with value = Yes
  - 4. Variable 7: at least 1 of Variables 1 and 2 is Yes
- iii. Each of the variables above are defined for two time periods
  - 1. T0 - T1 = before consent through date of consent into the study
  - 2. T1 - T2 = after consent through the end of the study
- iv. Endpoint: Variable 7, at least one of personal history code or family history code, Variables 1 and 2 respectively, are met
- v. Sensitivity Endpoints:
  - 1. Variable 1: Personal history code in EHR
  - 2. Variable 2: Family history code in EHR

- b. Genetic counseling appointment times

- i. Length of genetic counseling appointments

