### 3. Secondary Endpoint 1: EHR-based identification of hereditary risk pre- and post-MeTree

- a. **Hypothesis:**

- i.  $H_0$ : MeTree has no impact on identification of patients at high risk for hereditary cancer
- ii.  $H_A$ : MeTree impacts the identification of patients at high risk for hereditary cancer

- b. **Analysis:** Descriptive statistics (counts and percentages) will be used to describe the EHR-based indication for increased cancer risk (Variable 7: presence of a personal or family history codes) for the two study time periods: pre-study consent period (T0-T1) to the post-study consent period (T1-T2) within the effectiveness population. Contrast the EHR-based determination of high risk for cancer (Variable 7), between the pre-study consent period (T0-T1) to the post-study consent period (T1-T2) using the McNemar test for paired observations, test statistic and p-value will be reported.

**4. Secondary Endpoint 2:** Genetic counseling appointment length for participants who used MeTree and for randomly selected patients from the same clinic who did not use MeTree.

a. **Hypothesis:**

- i.  $H_0$ : Using MeTree prior to genetic counseling has no impact on genetic counseling appointment length
- ii.  $H_A$ : Using MeTree prior to genetic counseling affects genetic counseling appointment lengths

b. **Analysis:** Descriptive statistics (mean, standard deviation, median and IQR or counts and percentages) will be used to summarize appointment lengths by intervention group. Differences in genetic counseling appointment length between intervention groups will be assessed using the Wilcoxon rank sum test, p-value will be reported

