**6. Exploratory Sensitivity Analysis 2 (Personal Hx Code):**

a. **Analysis:** EHR-based indication for increased cancer risk based on personal history (Variable 1), contrasting the pre-study consent period (T0-T1) to the post-study consent period (T1-T2), in both the **Effectiveness and Reach populations**. McNemar test for paired observations will be used to compare high risk identification in the pre-study period to the post-study period.

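### Secondary Endpoint 1 would count a personal-history code for a cancer first diagnosed after consent as a gain in identification, which adds pairs to the McNemar gain cell that MeTree did not cause

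*SAP*

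**What the plan says.** SAP III.2.a introduces the outcome as "EHR-based indication for increased cancer risk, defined separate for the time periods". The personal-history component is given only as "Variable 1: Personal history code in EHR [Yes/No", with no code list and no condition on the date of the cancer. The endpoint itself is "Endpoint: Variable 7, at least one of personal history code or family history code, Variables 1 and 2 respectively, are met".

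The two windows are "T0 - T1 = before consent through date of consent into the study" and "T1 - T2 = after consent through the end of the study". The second opens at consent, not at the MeTree report. The SAP does not say whether a code from the first window carries into the second.

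SAP IV.3 applies McNemar's test to Variable 7 in participants who completed MeTree. The null is "MeTree has no impact on identification of patients at high risk for hereditary cancer" and the alternative "MeTree impacts the identification of patients at high risk for hereditary cancer". There is no concurrent control. SAP II.3.f limits EHR analyses to VUMC. The same contrast is repeated in the Reach population (IV.5), on Variable 1 alone (IV.6: "EHR-based indication for increased cancer risk based on personal history (Variable 1), contrasting the pre-study consent period (T0-T1") and on Variable 2 alone (IV.7).

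Protocol Section 8 describes a different post assessment: the MeTree report, measured when it is generated and regardless of length of follow-up.

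**The concern.** The hypothesis is about recognising risk that already exists. A cancer that first occurs during follow-up is a new event. If it produces a code that counts under Variable 1, a participant who was No before consent becomes Yes afterwards, whatever MeTree reported or whether it had yet reported anything. Protocol Section 7 allows up to 12 months to complete MeTree before removal from the study, so such a code can even precede the report.

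McNemar's test uses only the discordant pairs, so these cases go straight into the cell that favours MeTree. Nothing in the eligibility criteria or the analysis removes them, and they accumulate with time. Under the protocol's definition of the post assessment, cancers diagnosed later in follow-up could not enter. At stake is whether a significant result for a named secondary endpoint can be read as better identification.

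**Working it through.** **Inputs from the documents.** Protocol Section 8 gives a minimum of 3,000 completers over both sites, which reproduces: 150 / (0.10 × 0.50) = 3,000. Protocol Section 10 gives a study length of 4 years. Protocol Section 8 uses 0.05 in its power graph; the SAP states no alpha for this test, so I take two-sided 0.05.

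**Inputs that are assumptions.** The documents give no VUMC share, cancer incidence, follow-up per participant, proportion already coded at consent, or rate at which old codes are re-recorded. Unless stated otherwise I use 2,000-2,500 VUMC completers, 0.5-1.0% per year and 1.5-2 years.

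**Step 1. Upper count of added gains** = completers × incidence × years.
- Low: 2,000 × 0.005 × 1.5 = 15
- High: 2,500 × 0.010 × 2 = 50

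This counts all completers. Only those with no earlier Variable 1 or 2 code can become No-to-Yes. If 20% were already coded (assumption), the range is 12 to 40. It also assumes that every incident cancer yields a counted code.

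**Step 2. How many it takes to reject.** Let b be the No-to-Yes pairs and c the Yes-to-No pairs. The uncorrected statistic is (b − c)² / (b + c), with critical value 3.84.
- c = 0, exact test: b = 5 gives p = 2 × 0.5⁵ = 0.0625; b = 6 gives p = 2 × 0.5⁶ = 0.031. Six suffice.
- c = 50: b = 72 gives 22² / 122 = 3.97; b = 71 gives 21² / 121 = 3.64. So 22 extra (exact test: 23).
- c = 100: b = 130 gives 30² / 230 = 3.91; b = 129 gives 29² / 229 = 3.67. So 30 extra (exact test: 31).

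**Step 3. Examples with otherwise balanced cells (the balance is an assumption).**

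| Other pairs each way | Added gains | Statistic | p |
|---|---|---|---|
| 50 | 15 | 15² / 115 = 1.96 | 0.16 |
| 50 | 20 | 20² / 120 = 3.33 | 0.068 |
| 50 | 25 | 25² / 125 = 5.00 | 0.025 |
| 50 | 40 | 40² / 140 = 11.43 | 0.0007 |
| 100 | 25 | 25² / 225 = 2.78 | 0.096 |
| 100 | 40 | 40² / 240 = 6.67 | 0.010 |

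**Step 4. No lost codes and no MeTree effect.** Take c = 0 and 80% code-negative at consent. With 2,000 completers, 0.5% per year and 2 years, expected b = 2,000 × 0.8 × 0.005 × 2 = 16, and P(b ≥ 6) = 0.999. With 1,000 completers, 0.2% per year and 1 year, expected b = 1.6 and the probability is 0.006.

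**Step 5. Windows scored separately, as the text reads.** Take 2,000 completers, 10% coded before consent, 0.5% per year and 2 years. Expected gains are 1,800 × 0.01 = 18, and expected losses are 200 × (1 − re-recorded share). From 20,000 simulated trials, uncorrected test:

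| Earlier codes re-recorded | Expected losses | P(reject upward) | P(reject downward) |
|---|---|---|---|
| 100% | 0 | 1.00 | 0.00 |
| 99% | 2 | 0.98 | 0.00 |
| 95% | 10 | 0.33 | 0.00 |
| 90% | 20 | 0.01 | 0.05 |
| 80% | 40 | 0.00 | 0.85 |

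The same incident cancers can thus sit in a test that rejects for MeTree, does not reject, or rejects against it.

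**The case against.** A reader might infer that every new cancer creates a personal-history code and that background incidence by itself will reject H0 in MeTree's favour. The documents support neither. Without a code list, Variable 1 may hold only history-of codes, so that an active cancer is not scored or is scored late. With separate, unequal windows and no carry-forward rule, earlier codes that are not re-entered become losses, which can offset or reverse the effect. Nor can incidence be taken as high because of age: eligibility is 18 or older and no age distribution is given.

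It is also fair to say that IV.7, on family-history codes alone, avoids the problem, that comparing IV.3, IV.6 and IV.7 would show whether personal-history codes drive the result, and that the affected test is secondary, since the SAP primary endpoint has no inference.

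These points limit the size and direction of the claim, but the gap remains. Nothing in the SAP excludes a counted code for a post-consent cancer. IV.7 is exploratory and Variable 7 stays the endpoint. Losses that happen to mask spurious gains do not make the test valid. If earlier codes are carried forward to repair the losses, c becomes zero and six incident cases suffice.

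**Conclusion.** The point holds as a defect in the definition of Secondary Endpoint 1 and should be fixed. As written, a counted Variable 1 code for a cancer first diagnosed after consent, in a participant with no earlier Variable 1 or 2 code, is a gain wrongly attributed to MeTree. The inflation is at most about 15-50 pairs under the Step 1 assumptions, and smaller after removing those already coded or if some incident cancers do not receive a counted code. Its effect on the p-value depends on the number of Yes-to-No pairs, which the documents do not let us estimate, so neither a false-positive rate nor a net direction can be stated. Until the SAP settles the codes, the diagnosis dates and the carry-forward rule, a significant McNemar result cannot be attributed to MeTree.

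**What to change.** In SAP III.2.a:

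1. List the codes that make up Variable 1, and say whether an active-cancer diagnosis is among them.
2. Do not count a T1-T2 Variable 1 code toward Variable 7 when the documented diagnosis date of that cancer is after consent. Use the diagnosis date, not the date of first EHR entry; otherwise an older cancer treated elsewhere and first recorded through MeTree, a true gain in recognition, would be dropped.
3. Keep codes for cancers that pre-date consent, and all family-history codes.
4. State that pre-consent codes carry into T1-T2, so that earlier identification is not scored as lost and the exclusion does not trim only the gain cell.

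Apply these rules in IV.3, IV.5 and IV.6 (in IV.6 to Variable 1 itself). Report the number of codes removed, and show each result with and without the exclusion.

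The cost is SAP wording, one extra EHR date field, a rule for uncertain diagnosis dates, and slightly fewer post-consent positives. Two limits should be stated in the SAP. With carry-forward there are no Yes-to-No pairs, so the test can only move upward, and the count of new identifications should be reported beside the p-value. The exclusion also removes only this source of gains: without a concurrent control, codes added in ordinary care after consent still count.

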## 3. Handling of Missing Data

Data will be analyzed as captured in the redcap surveys and in the MeTree database. Missing data will not be imputed. In the MeTree relative conditions data, the absence of a condition will be assumed to be “no” if the health history is not set to “unknown.” If health history is unknown, the condition will be set to “NA.” Analysis reports will be programmatically generated from processed MeTree data cuts.

## IV. STATISTICAL ANALYSIS

### 1. Analysis Objectives and Tasks

- a. Describe the Reach populations

- i. **Analysis:** Descriptive statistics (counts and percentages, mean, median, standard deviation, IQR range) will be used to describe the demographics and baseline characteristics of the **Reach population**. Statistical tests: fisher's exact test, chi-square test, or wilcoxon ranked sum test will be used to identify differences between the participants who completed MeTree (Effectiveness population) and did not complete MeTree within the Reach population

- b. Describe the genetic counseling populations

- i. **Analysis:** Descriptive statistics (mean, standard deviation, median and IQR or counts and percentages) will be used to describe differences in demographics by intervention group, MeTree and standard of care. Difference between groups will be assed via Wilcox rank sum test or fisher's exact test.

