The practice of genetic medicine is changing as genetic discoveries are translated into new tests for an increasing number of health indications. In fact, the prevalence of high-risk individuals who are at risk for hereditary cancer has been rising due to new testing strategies. This has placed enormous pressure on the hospitals and clinics providing care for high-risk patients. Coupled with the healthcare system's need for greater efficiency, the traditional genetic clinic-based practice has become untenable. Barriers and challenges include low numbers of trained genetic workforce, lack of integrated FHH platforms for patients and physicians, and long wait times for available clinic appointments. Further, while cancer syndromes are seen across all groups, gaps in care exist as underserved populations are often not recognized and referred for care.

MeTree is a computer platform that has been developed by researchers at Duke University that electronically collects FHH information for hereditary cancer syndromes and other health conditions directly from the patient. MeTree then calculates hereditary cancer risks for the patient and creates a personalized patient report and evidence-based clinical decision support for the provider. In previous studies, MeTree demonstrated improvements in the identification of those at risk and highlighted ongoing challenges particularly around undergoing genetic counseling and testing, and awareness of risk. Co-investigators from Duke/MeTree collaborate on this grant.

2. Rationale and Specific Aims

SA1. Deploy a care delivery model that will facilitate systematic risk assessment for hereditary cancers in diverse clinical environments.

- Up to 3,500 participants will be enrolled and complete the MeTree FHH risk assessment
- Deploy in 2 academic medical centers; Vanderbilt University Medical Center (VUMC) and Meharry Medical College (MMC)
- Assess participants perceptions using online survey and qualitative semi-structured interviews

SA2. Improve access to genetic healthcare providers for participants at risk for hereditary cancer syndromes.

- 300 high risk participants in the VUMC Hereditary Cancer Clinic will be enrolled
- Extend clinic capacity by lessening the need for in-clinic family history collection and basic counseling
- Expand reach of clinic by using telephone and video genetic counseling; referral to specialists

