As described in Section 4, participants will be recruited and enrolled electronically. * This process will take approximately 30-45 minutes, depending on the answers to screening questions. Once enrolled, they will be asked to complete the MeTree Family Health History (FHH) questionnaire (See Appendix A for actionable conditions, Appendix B for actionable recommendations, Appendix C for MeTree participant report example, and Appendix D for MeTree provider report example).

Upon entry into the MeTree platform, participants will be able to immediately enter FHH information into the program or download the worksheet for collecting the information requested by MeTree from family members and return later to enter the information into the MeTree platform (The printable worksheet is named Appendix E). The time involved to complete MeTree may vary significantly depending upon the number of relative's participants enter data on and the availability of the FHH information. This will be mitigated by providing a smart link to finish the FHH in pieces, rather than all at once. Participants are advised in the consent form that answering the FHH questions may make them uncomfortable.

For participants who may want additional instructions for the MeTree questionnaire, we will provide a how-to power point (included as Appendix F).

Vanderbilt: Participants who do not access MeTree within 30 days of consent will be sent reminder emails once per week for up to 4 weeks. Once participants complete data entry in MeTree and the post-MeTree survey, participants will be sent a \$20 gift card. Participants will be sent a web-based survey via an email link 4 to 6 weeks after completing MeTree (post-MeTree survey). If the survey is not completed within 1 week of the initial invitation, reminder emails will be sent weekly for up to 4 weeks. Participants will receive a \$20 gift card for completing the post-MeTree survey.

[name]
U01-CA232829-01A1
FOREST

Meharry: For enrolling and completing the baseline (pre-MeTree) survey, participants will receive \$10 cash (if on site) or Amazon or Visa gift card (sent to your home). For the completion of the MeTree questionnaire, participants will receive an additional \$50 cash (if on site) or gift card. Participants may receive \$10 cash or gift card for any additional surveys after completing the MeTree questionnaire.

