### 3. Analytical Population(s)

- a. **Reach population:** defined as the participants who were invited to use MeTree (completed baseline surveys and clicked link to use MeTree)
- b. **Effectiveness population:** defined as the participants who completed MeTree and had a clinical decision support risk report generated.
- c. **Genetic counseling population:** The genetic counseling population includes participants who completed MeTree, received a genetic counseling recommendation and completed the genetic counseling appointment. A random selection of non-study participants with genetic counseling appointments at the same clinic and in the same time frame will be selected, 1:1.
- d. See the protocol paper for additional details of these populations:  
<https://www.sciencedirect.com/science/article/pii/S1551714424002970#f0010>
- e. Study participants had to meet the following inclusion and exclusion criteria to be enrolled in the FOREST study:
  - i. Inclusion
    1. Site: VUMC, MMC
    2. Demographics: Age 18 years or older
    3. Able to read and communicate in English
    4. Willing and able to use the internet to report FHH information
    5. Current user of patient portal (VUMC specific)
  - ii. Exclusion
    1. Not a patient at VUMC or MMC sites
    2. Diagnosed with a terminal illness
    3. Unable to speak/read English
    4. Unwilling or unable to use the Internet to report their FHH information
    5. Report previous genetic testing and/or counseling through the VUMC Hereditary Cancer Clinic
- f. Analyses involving EHR -related information will be restricted to VUMC participants due to the specificity of the EHR-based outcomes.

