### 2. Primary Endpoint: Completion of MeTree

- a. Implementation endpoint: Report the number and percentage of participants who completed MeTree out of the reach population. As single-arm implementation endpoint, no inferential statistics will be used.

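### The SAP tests who fails to complete MeTree one characteristic at a time on pooled sites; a site-adjusted comparison should be added beside the crude table

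*SAP*

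**What the plan says.** The primary outcome is completion of MeTree. It is reported as one number and percentage of the Reach population, and the SAP adds: "As single-arm implementation endpoint, no inferential statistics will be used" (SAP IV.2). Reach is "defined as the participants who were invited to use MeTree (completed baseline surveys and clicked link to use MeTree" (SAP II.3.a) and takes in both sites.

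The only analysis of who does not reach that outcome is SAP IV.1.a. Descriptive statistics "will be used to describe the demographics and baseline characteristics of the" Reach population, and then "fisher's exact test, chi-square test, or wilcoxon ranked sum test will be used". These tests are "used to identify differences between the participants who completed MeTree (Effectiveness population) and did not complete MeTree within the Reach population". The section gives no list of variables, regression model, stratification or completion rate by site. The SAP's only analysis rule about site restricts EHR-based analyses to VUMC (II.3.f), which does not cover completion.

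Protocol section 5 sets different payments. For Meharry: "For the completion of the MeTree questionnaire, participants will receive an additional" $50, in cash if on site. For Vanderbilt, a $20 gift card follows once both MeTree and the post-MeTree survey are done, and that survey goes out 4 to 6 weeks after MeTree. The Vanderbilt paragraph mentions $20 twice, so it may mean one payment or two; the terms differ from Meharry's on either reading.

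**The concern.** A payment tied to completing the questionnaire is a plausible reason for completion to differ by site. If the sites also enrol different kinds of people, a pooled test on any characteristic that is unevenly spread across sites picks up part of the site difference. A reader could then credit or blame a group for something that belongs to how MeTree was delivered to it, or could miss a shortfall present at both sites.

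This bears on how the results will be used. Aim 1 is about deployment in diverse clinical environments, and the protocol background says that "gaps in care exist as underserved populations are often not recognized and referred for care". That sentence concerns clinical recognition and referral, not questionnaire completion, but a table of who did not complete will naturally be read in its light.

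**Working it through.** The documents state no figure for this comparison, so there is none to reproduce. The calculation below only illustrates size.

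**Assumed inputs (none from the documents, except that the total equals the protocol's upper enrolment target of 3,500).** Reach has 2,500 at VUMC and 1,000 at Meharry. A trait is held by 15% at VUMC (375) and 75% at Meharry (750), so 1,125 have it and 2,375 do not (2,125 and 250). Completion without the trait is 60% at VUMC and 60% plus the site gap at Meharry.

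**Formula.** When the within-site gap is the same at both sites:

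crude gap = within-site gap + (difference in Meharry share between groups) × (site gap)

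Meharry share with the trait: 750/1,125 = 66.7%. Without it: 250/2,375 = 10.5%. Difference: 56.1 points.

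The pooled test is the 1-df chi-square without continuity correction on expected counts, X² = (p1 − p2)² / [p(1 − p)(1/n1 + 1/n2)], two-sided. The SAP states no significance level for these tests.

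**Results.**

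- *Site gap 10, no within-site difference.* With trait: (375×0.60 + 750×0.70)/1,125 = 66.7%. Without: (2,125×0.60 + 250×0.70)/2,375 = 61.1%. X² = 10.3, p = 0.001. Site-stratified odds ratio 1.00.
- *Site gap 15, trait 10 points lower at each site.* With trait: (375×0.50 + 750×0.65)/1,125 = 60.0%. Without: (2,125×0.60 + 250×0.75)/2,375 = 61.6%. Pooled p = 0.37; Cochran-Mantel-Haenszel (CMH) p < 0.001.
- *Site gap 5, no within-site difference.* 63.3% vs 60.5%, p = 0.11.
- *Reversal.* The sign of a 10-point deficit flips when the site gap exceeds 10/0.561 = 17.8 points. At 20 points the flipped gap is small and not significant (63.3% vs 62.1%, p = 0.48). At 25 points it is 66.7% vs 62.6%, p = 0.02 in the opposite direction, with crude odds ratio 1.19 against a stratified 0.63 (95% CI 0.52 to 0.76).

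**Sensitivity to the assumptions.**

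- *Fewer at Meharry.* With 300 of 3,500 there and the same prevalences, the Meharry shares are 225/705 = 31.9% and 75/2,795 = 2.7%. Reversal then needs about 10/0.292 = 34 points.
- *Milder mix.* With 2,500 and 1,000, a 15-point site gap and no within-site difference, prevalences of 15% and 40% give pooled p = 0.023. Prevalences of 30% and 50% give p = 0.11.
- *No distortion.* If mix or completion is the same at both sites, the second term of the formula is zero and the crude gap equals the within-site gap.

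A second set of assumptions (N = 3,000; trait in 12% and 80%; site gap 10 points; no within-site difference; 4,000 simulated runs per scenario) shows how often each test is significant at 0.05. The pooled test is significant in 43%, 71% and 96% of runs with 300, 500 and 1,000 at Meharry. The CMH test stays between 4.6% and 4.9%. These pooled rates are not errors about the overall difference, which is real in those scenarios. They show how often a reader would wrongly infer a within-site difference.

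**The case against.** The strongest reply is that IV.1.a is headed as description and states no hypothesis, whereas both secondary endpoints have a null and an alternative. The crude comparison answers how completers differ from non-completers in Reach as a whole, and it is the relevant table for seeing how the Effectiveness population departs from Reach. This stands. A reader might infer that pooling invents gaps or makes the tests invalid. The documents do not support that: a pooled difference is a true overall difference, and the pooled test correctly detects it. The fault arises only if it is read as a difference between groups given the same delivery.

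A reader might also infer that the VUMC-only portal criterion, the recruitment route and the Vanderbilt reminders all drive completion. Reach begins after the baseline surveys and the click on the link, and the reminders described go to people who have not accessed MeTree. These features therefore act mainly before entry to Reach, and Meharry's recruitment route is not set out. The payment difference is what remains, and no document says how large a completion gap it produces or in which direction.

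A reader might further infer that reversal is to be expected. It needs a large site gap and a sizeable Meharry share, neither of which the documents give.

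Site might be tabulated among the unlisted baseline characteristics. That would reveal a site gap, but it would not adjust any other comparison.

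**Conclusion.** The point holds as a low-cost improvement. The only SAP analysis of who does not complete MeTree cannot separate a characteristic from the site its holders come from, and the sites differ in a payment tied to the outcome. Whether this matters depends on mix and completion both differing by site, which cannot be judged from the documents. On the assumed figures the effect ranges from little (5-point site gap) to a hidden 10-point deficit (15-point site gap). Nothing here calls the primary percentage or either secondary endpoint into question.

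**What to change.** In SAP IV.1.a:

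- List the baseline characteristics to be compared, and keep the crude table as description.
- Report completion by site, and by level of each characteristic within site.
- Add a site-adjusted comparison. Use either CMH tests for categorical and van Elteren tests for continuous characteristics, or one logistic regression of completion on site and the baseline characteristics already collected. Give odds ratios with 95% confidence intervals.
- Check for characteristic-by-site interaction, because a common effect could mask opposite gaps at the two sites.
- State that any conclusion about which groups complete less often rests on the site-adjusted results.

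The cost is SAP wording and a little programming, with no new data. The downside is that some site-by-group cells will be small and their intervals wide.
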